After reviewing eligibility criteria as described above, a study team member will go to the Emergency Department (ED) at HMC. First, appropriateness of the study for the participant will be determined by discussing with a member of the care team if possible (e.g. physician or nurse) and determining if the patient has an appropriate mental status for screening. The study team member will then introduce themselves to the patient and gauge interest in hearing more about the screen. Specifically, the study team member will let the patient know that they are here with 'ED-LINC, a project being conducted out of the Emergency Department at Harborview and can I ask you a few questions to see if you are a good fit for our project'. Once verbal consent is obtained, the study team member will proceed with self-report screening which includes the NIDA m-ASSIST for illicit opioids and prescription opioid misuse.¹⁰ Participants who endorse any use of illicit opioids and/or misuse of prescription opioids in the past 3 months AND have a score of ≥ 4 on the ASSIST are eligible for enrollment.

A member of the research team will then complete the patient eligibility summary (PES) that includes the following:

- NIDA modified-ASSIST for illicit opioids or prescription opioid misuse is ≥ 4 (**yes/no**)
- Between 18-65 years old (**yes/no**)
- English speaking (**yes/no**)
- Medical or injury complaint (e.g. not psych) (**yes/no**)
- Current address is within 50 miles of HMC and valid for six months (**yes/no**)
- Has a cell phone or phone number (**yes/no**)
- Can provide one additional contact (**yes/no**)
- Not currently receiving hospice or palliative care (**yes/no**)
- Currently receiving prescribed opioids from a physician for most days out of 90 (**yes/no**).

If all answers in the PES confirm eligibility, the potential participant will be offered the opportunity to hear more about the study. If the patient has a NIDA m-ASSIST score for illicit opioids or prescription opioid misuse ≥ 4 but is otherwise ineligible, they will be provided a resources list (see Resources Hand Out). More information on informed consent can be found in Section IV Human Subjects Protocol.

C. Obtaining written Informed Consent for those with positive OUD screen and confirmed eligibility on the PES

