The study team member will provide an overview of the study and provide an unsigned copy of the informed consent to the potential participant, allowing ample time to read. If the patient is interested in participating, the study team member will review the informed consent verbally with the participant, answer any questions and obtain a signature on the consent form located in RedCap. If a patient does not want to consent to the study, the study team member will politely inquire rationale behind the refusal and this will be tracked as part of the main outcome related to feasibility. In previous studies, reasons for refusal at this point have included 'too much pain', 'not interested', 'do not want to do follow-up surveys and/or other study procedures' and 'discharged and don't want to wait'.

D. Randomization

After participants have undergone informed consent, the randomization procedure will take place. The investigation will employ a blocked randomization strategy with random assignment of block size of either 4 or 6 participants. Randomization will also be stratified by inclusion for prescription opioid misuse based on a NIDA m-ASSIST score of ≥ 4 for prescription opioid misuse. It is hypothesized that the majority of participants will screen in for illicit opioid use and stratified randomization will be used to ensure balance of participants with prescription opioid misuse given this is an important but likely small population of participants. Participants will be randomized to the following conditions:

- a. Usual Care control condition
- b. ED-LINC 2.0

Study condition will be assigned using the RedCap randomization module which will be programmed prior to study start by a data analyst. After the study team member obtains informed consent, randomization of condition will be performed using RedCap and the participant will be notified of their random assignment.

E. Baseline Interview

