Medications and pharmacotherapy is an important part of collaborative care. It is hypothesized that many patients will not have primary care and might be experiencing fragmented health care delivery. The pharmacotherapy element will be guided by the principle of ultimately linking to care. First, the RC will address the need for coordinated care. After conducting the BNI (above) The RC will step away from the patient and have a conference with one of the supervisory physicians of the study team. In-line with published HMC protocols, the RC will have a conversation with the participant about take-home naloxone. This conversation will be tailored to participant risk for overdose based on their use of illicit opioids, misuse of prescription opioids or both. Naloxone is distributed in many locations around Seattle without a prescription based on pharmacy collaborative agreements. If the participant desires a prescription, the RC will talk with the treating clinical team or the study physicians.

Next, for participants with prescription opioids, the RC will discuss safely storing prescription opioids and safe disposal of prescription opioids. This conversation will be

guided by resources published on stopoverdose.org and med-project.org which are publically available materials.

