Lastly, the study physicians in coordination with the RC will discuss medication assisted treatment for participants with risk for opioid use disorder secondary to illicit opioids. It is recognized that opioid agonist treatment improves outcomes for patients with opioid use disorder (OUD)¹⁶ and patients with OUD that initiated buprenorphine in the ED had improved engagement in treatment at 30 days compared to those that received only BNI or standard care.¹ Therefore study participants will be assessed for willingness for opioid agonist treatment. If participants are interested in opioid agonist treatment, the RC will discuss this with both the treating clinical team and study physicians. Based on the patients clinical course, this can be managed by the treating clinical team (e.g. patient is getting care inpatient, patient is in the ED) or the study physicians (e.g. patient is already discharged) or the study physician will offer to coordinate with the treating clinical team (e.g. patient is in the ED). Initiating buprenorphine from the ED for patients with opioid use disorder is an evidence-based treatment¹ with recently published guidelines.¹⁷ Specifically, participants will be screened for opioid withdrawal using the clinical opioid withdrawal scale (COWS)¹⁸ and if they are in moderate or severe opioid withdrawal the RC and study physicians will communicate this with the treating clinical team and the treating clinical team can offer one dose of buprenorphine dispensed from the ED to treat withdrawal if this is clinically appropriate. If the participant is not in moderate or severe withdrawal, or if the participant has already discharged from the ED, the study physician can determine appropriateness for a home induction of buprenorphine with appropriate transition to an outpatient based opioid treatment (OBOT) clinic. We anticipate that many patients that do not have a PCP will be appropriate for the HMC After Care clinic or the Adult Medicine Clinic although there are several community clinics around Seattle which will offer continued buprenorphine and there are several local places that will dispense buprenorphine or initiate buprenorphine with low barrier or same-day service. A list of clinics offering buprenorphine for OUD has been compiled. While all efforts will be made to link to an outpatient buprenorphine provider as described above, it is a known risk of initiating any medication including buprenorphine from the ED that some patients will fail to link to care. This risk is part of the standard of care of initiating treatment from the ED for any condition. Specifically, failing to link to care after initiation of buprenorphine could result in opioid withdrawal. Some participants will be interested in other types of opioid agonist treatment such as methadone or naltrexone and the RC will discuss this request with the treating clinical team if appropriate (e.g. inpatient) and provide coordination to a opioid treatment provider that can provide this service after the ED visit as part of the 'longitudinal care management' element. Participants in the ED-LINC condition that are already linked to opioid agonist treatment will work with the RC to strengthen these connections. It is anticipated that eligible participants that report engagement in opioid agonist treatment will require strengthened linkages and potential dose adjustments. These dose adjustments will likely occur by the prescribing provider.

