Follow-up Completion Rates were calculated for each followup timepoint and were calculated as the number of participants that completed follow-up divided by the total number of participants randomized to each arm of the trial. The 6-month followup completion rate is shown as the number of participants that completed the 6-month self-report interview divided by the number of participants randomized to each arm.

ED-LINC Intervention and usual Care process Outcomes were determined from extensive research notes. Specifically the EDLINC interventionist conducted a process validity assessment and documented the number of unique ED-LINC elements completed for each participant in the intervention.

Implementation Appropriateness was calculated by providing this validated self-report measure to each participant randomized to the ED-LINC assessment. Results were dichotomized to calculate the frequency of participants who 'agreed' or 'completely agreed' that the intervention was 'applicable' and 'seemed like a good match' to document appropriateness.

Satisfaction was calculated using a validated satisfaction questionnaire and provided to all participants at six-months. Each participant will complete the questionnaire and their results will be summed. The median and IQR range will be calculated for participants in each group that complete the assessment.

Perception of Care Coordination will be done using questions from a validated scale. The Wilcoxon Rank Sum test will be used to determine if there are significant differences between groups.

Secondary Outcome Measures

Substance Use

Substance use will be measured using the timeline follow back procedure which is a validated calendar method to determine days of use in a certain calendar period. First, we will sum days of use of illicit opioid use in 30 days at baseline and each followup period for each participant. The mean days of use/30 days with an associated standard deviation will be calculated at each time-period for both the ED-LINC intervention and the usual care control groups.

Next, we will evaluate variance of the data and test model fit on unadjusted data using different distributions. Given previous work, we anticipate the data to be skewed and zero-inflated. Thus, we hypothesize that we may use a normal Gaussian, Poisson or negative binomial distribution.

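### The stratum balances prescription opioid misuse as a whole but only partly protects the prescription-only subgroup, and the SAP model for illicit-opioid days guarantees no adjustment for that subgroup.

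*Protocol*

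**What the plan says.** **Stratum.** Protocol III.D uses blocks of 4 or 6 and one stratification factor: "Randomization will also be stratified by inclusion for prescription opioid misuse based on a NIDA m-ASSIST score of ≥ 4 for prescription opioid misuse". No condition is placed on the illicit-opioid score.

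**Purpose.** The same paragraph expects most participants to enter through illicit use ("It is hypothesized that the majority of participants will screen in for illicit opioid use") and stratifies to "ensure balance of participants with prescription opioid misuse given this is an important but likely small population of participants".

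**Overlap.** Protocol III.B admits either route or both: "Participants who endorse any use of illicit opioids and/or misuse of prescription opioids in the past 3 months AND have a score of ≥ 4". The Pharmacotherapy section likewise tailors the naloxone conversation to "their use of illicit opioids, misuse of prescription opioids or both". No expected number is given for prescription-only or dual participants.

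**Outcome.** Under Substance Use, the SAP states that "we will sum days of use of illicit opioid use in 30 days at baseline and each followup period". It then describes reverse stepwise selection from clinician-chosen inputs, together with intervention and timepoint, dropping terms with p above 0.05. Neither the stratification factor nor entry route is named as a term to be kept.

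**The concern.** Someone scoring 4 or more on both scales shares a stratum with someone scoring 4 or more on the prescription scale alone. Blocking fixes the total in that stratum by arm. It does not fix how the total divides between the two kinds of participant.

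For the SAP's substance-use outcome, that division matters. A prescription-only participant should contribute few or no illicit-opioid days, while a dual user should look more like the illicit-only majority. An uneven split of prescription-only participants therefore moves the arm means with no treatment effect.

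The split also bears on intervention content, because the Protocol says the study physicians "will discuss medication assisted treatment for participants with risk for opioid use disorder secondary to illicit opioids". It thus affects how many in the ED-LINC arm are in line for that discussion.

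**Working it through.** **Inputs.** From the documents: 1:1 allocation, blocks of 4 or 6, N = 40 (SAP) or 60 (Protocol). The documents state no stratum size or expected balance, so there is no plan figure to reproduce. Assumed: K prescription-only and d dual participants, at several values.

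**Imbalance under the written rule.** Let M = K + d be the size of the shared stratum and D the between-arm difference in prescription-only counts. If the stratum splits evenly and enrolment order is random, the prescription-only count in one arm is hypergeometric, so

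Var(D) = K(M − K)/(M − 1) = K·d/(K + d − 1).

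This is zero when d = 0 and rises with d. For K = 6, d = 12:

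- Var(D) = 72/17 = 4.24, so SD = 2.06.
- P(|D| ≥ 4) = 2 × [C(6,5)·C(12,4) + C(12,3)]/C(18,9) = 2 × (2,970 + 220)/48,620 = 0.131.

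The simulated values below use the actual random blocks at N = 40. They run slightly higher because a last block may be incomplete. The unstratified column uses the same formula with M = 40.

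| K + d | SD(D), formula | SD(D), simulated | P(difference ≥ 4), formula | P, simulated | P, unstratified |
|---|---|---|---|---|---|
| 6 + 6 | √(36/11) = 1.81 | 1.87 | 74/924 = 0.080 | 0.090 | 0.182 |
| 6 + 12 | √(72/17) = 2.06 | 2.07 | 0.131 | 0.135 | 0.182 |
| 6 + 18 | √(108/23) = 2.17 | 2.17 | 0.155 | 0.156 | 0.182 |
| 8 + 12 | √(96/19) = 2.25 | 2.29 | 31,372/184,756 = 0.170 | 0.180 | 0.235 |

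With K = 6 a difference of 4 or more means 5:1 or 6:0. With no dual users the probability is 0.000; with 3 it is 0.046 (N = 40) or 0.059 (N = 60). N = 60 otherwise gives nearly the same: 0.087 for 6 + 6 and 0.153 for 6 + 14.

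**Balance of the group the Protocol names.** For everyone with a prescription score of 4 or more, the written rule gives P(difference ≥ 4) = 0.000 in every scenario.

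**Effect on illicit-opioid days.** Assume prescription-only participants have 0 days and all others average μ of 30. With 20 per arm, each net participant shifts the arm difference by μ/20, so the chance component has SD (μ/20) × SD(D). For 6 + 12 and μ = 15 this is 0.75 × 2.06 = 1.55 days.

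**What adjustment recovers.** Assume the 34 other participants have SD 8 days. Their contribution to the variance of the arm difference is 34 × 64/400 = 5.44 (SD 2.33), with or without the indicator. The indicator removes the chance component:

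| μ (assumed) | Unadjusted SD | Adjusted SD | Reduction |
|---|---|---|---|
| 5 | √(5.44 + 0.27) = 2.39 | 2.33 | 2% |
| 10 | √(5.44 + 1.06) = 2.55 | 2.33 | 9% |
| 15 | √(5.44 + 2.39) = 2.80 | 2.33 | 17% |
| 20 | √(5.44 + 4.24) = 3.11 | 2.33 | 25% |

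A separate simulation of 6 + 6, 6 + 12 and 8 + 12, under its own assumed use rates, gave reductions of about 13 to 20%, for example 2.50 to 2.18 days. The component removed in that example is √(2.50² − 2.18²) = 1.22 days, which in 6 + 12 corresponds to μ of about 1.22 × 20/2.06 = 12 days.

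**The case against.** **The rule does what it says.** A reader might infer that the stratification misses its own target. The text does not support that. The group named is participants with prescription opioid misuse, defined by the prescription score, and that group is balanced. Prescription-only status can be read into the contrast with the illicit majority and into the phrase about a small population, but it is not stated. This objection stands in full.

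**The subgroup is not left to chance.** That reading is also tempting and too strong. Blocking in the shared stratum keeps imbalance below the unstratified level in every scenario run, and there is no problem if no dual users enrol. This stands too, although the protection thins as dual users increase (0.156 against 0.182 in the 6 + 18 case).

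**Re-stratifying on prescription-only against any illicit use is not a clean repair.** It brings the subgroup's figure to 0.000. Among everyone with a prescription score of 4 or more, however, it raises P(difference ≥ 4) from 0.00 to 0.21 (6 + 6), 0.30 (6 + 12) and 0.31 (8 + 12). That trades away the balance the Protocol asks for. A three-level stratum avoids most of this (0.000 to 0.022), but the September 2021 SAP describes the trial in the past tense, so allocation is presumably complete.

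**The stakes are limited.** The primary outcomes are feasibility measures analysed descriptively, and the study is declared not powered for differences. Chance imbalance costs precision; it is not bias. Baseline illicit days are collected, and a model conditioning on them would absorb much of the imbalance. The SAP does not commit to that, so the gap in the model remains.

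**Conclusion.** A minor point that holds in limited form. The randomisation rule is sound for the group it names. It does not distinguish prescription-only from dual participants, so the prescription-only subgroup is partly protected, to a degree that depends on a dual share the documents do not give. In the 6 + 6, 6 + 12 and 8 + 12 scenarios at N = 40, prescription-only counts differ by 4 or more in about 9 to 18% of allocations.

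The consequence is confined to the illicit-opioid-days comparison, where the stepwise model may leave the imbalance unadjusted. Its size rests on three assumptions: the group sizes, near-zero illicit days in people with an illicit score below 4, and the average and spread of days among the rest. If illicit users average only about 5 days, the gain from adjustment is negligible.

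**What to change.** - Keep the randomisation rule as written.
- Report counts of prescription-only, dual and illicit-only participants by arm in the baseline table.
- In the illicit-opioid-days model, include an indicator for prescription-only status (prescription m-ASSIST of 4 or more and illicit m-ASSIST below 4), specified in advance and exempt from stepwise elimination. The SAP still words this analysis in the future tense. If it has already been run, present the adjusted result as a labelled sensitivity analysis.

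Both scores are collected at screening, so no new data are needed. The cost is one degree of freedom. If the SAP settles on a Poisson or negative binomial model and the subgroup has almost no illicit days, the indicator's coefficient may be unstable or fail to converge. The SAP should name a fallback, such as a linear model with the same indicator.
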